- Partner's vasectomy (if patient was exposed to vasectomy, nevertheless barrier contraception method should be applied).

Female patients of childbearing potential before the start of the study should be informed about importance of birth control measures during the study, potential risk factors associated with pregnancy occurrence and, moreover, that in case of pregnancy occurrence they should immediately inform investigator physician. Female patients, not having menstruations for 2 years and more before inclusion into the study, as well as female patients subjected to surgical intervention (surgical sterilization, bilateral ovariectomy, hysterectomy etc) are considered as female patients without childbearing potential. These patients may be free from requirements concerning contraception described above.

Male patients, participating in the study, should be also informed, that in case of pregnancy appearance in their female partners they have to notify Investigator physician about this circumstances.

Patient is issued the diary where he/she should make notes concerning number of urination episodes, number of incontinence episodes at daytime (from 7 am to 11 pm) and nighttime (from 11 pm to 7 am), number of awakenings, number of micturition urgency episodes, as well as administration/missing doses of the study product and adverse events.

Investigator explains to the patients rules for diary filling, schedules next visit date and requests for daily filling of diary and reminds to take the diary to the next visit.

4.5.3.2 Visit 2 (Randomization/Beginning of the therapy): Day 1

During the Visit 2 patient's conformity towards inclusion/non-inclusion criteria is repeatedly verified by Investigator. Patient, conforming to the inclusion criteria and not possessing non-inclusion criteria, randomly assigned into correspondent therapy group by randomization procedure (according to Section 4.3.1).

Randomization day and day of start of therapy are designated to be Day 1 and is considered to be baseline point for calculation of following visits schedule.

Prior to randomization:

Patient fills out OAB Awareness Tool Questionnaire and Quality of life Questionnaire EQ-5D.

Check up of diary filling results is performed.

Assessment of concomitant therapy, physical examination with BP and HR assessment, adverse events assessment and registration is performed.

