4.5.5.6 Questionnaires, filled up by the patients

Questionnaire for hyperactive bladder symptoms assessment (OAB Awareness Tool) and health assessment questionnaire EQ-5D are to be filled by patients. EQ-5D questionnaire is to be completed during randomization (Visit 2) and after the end of therapy (Week 12, Visit 6). Questionnaire for hyperactive bladder symptoms assessment (OAB Awareness Tool) is filled out during screening for verification of inclusion criteria and during Visits 2, 3, 4, 5 and 6.

These questionnaires are required to be filled out at the beginning of the visit before discussion with the patient and performance of other visit procedures. Patient should be provided with sufficient amount of time for answers to the questions. Questionnaires should be filled out in quite place without any distracting factors. Completed questionnaire is passed from the patient to Investigator, then Investigator verifies comprehensiveness and accuracy of it filling. The investigator transfers the filled questionnaires data into the CRF.

4.6 Description of “rules for study cessation” and “inclusion criteria” for individual subjects, parts of the study and study in a whole.

Sponsor of the study, R-Pharm JSC, shall reserve the right for termination of the study anytime for reasons, including but not limited to safety problems, ethical aspects or major protocol violations (see also Section 5.3).

Moreover, R-Pharm JSC, shall reserve the right to stop the study anytime if study goals are considered to be inaccessible.

However, the Sponsor shall notify the Principal Investigator and the Head of Medical Institution concerning premature termination of the study in written form.

If the study is terminated for reasons connected to safety problems, R-Pharm JSC shall immediately notify about these circumstances all Principal Investigators and regulatory authorities and ethical boards as well.

In cases when the Principal Investigator prematurely terminates the study before its end in his/her clinical center, he or she shall immediately notify the Sponsor concerning its ceasing with explanation provided.

Moreover, the study may be terminated under requirement of regulatory authorities or ethics board for reasons, including but not limited to safety problems, in accordance to the Russian Federation and the Belarus Republic legislation.

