9.8 Efficiency assessment

Efficiency assessment of mean daily, mean daytime and mean nighttime number of urinary incontinence episodes / urination at the Week 2, 4, 8 and 12 Visits, including analysis based on primary efficiency criteria, as well as mean number of urinary incontinence episodes per week at the Week 12 – will be performed with the use of covariance analysis (ANCOVA). Number of urinary incontinence episodes / urination at the Visit of start of therapy will be used as covariate, and therapy group will be used as factor. Primary efficiency analysis according to primary efficiency criteria will be performed in FAS and PP populations. For evaluation of hypothesis of “non-inferior” efficiency upper border of one-side 95% confidence interval for difference in evaluation of mean daily number of urinations among test product and control product tolterone will be calculated. During comparison of therapy groups according to other efficiency criteria two-sided 95% confidence intervals will be built. Comparison of therapy groups on efficiency criteria: change in Overactive Bladder Awareness Tool Questionnaire (OAB Awareness Tool) and change in Quality of life by Quality of life Questionnaire EQ-5D will be performed following data validation concerning their normality, distribution using Kolmogorov-Smirnov criteria. In case of normal distribution data will be compared using Student’s t-test, otherwise non-parametric Mann-Whitney criteria will be used.

Primary efficiency analysis according to secondary efficiency criteria will be performed in FAS and PP populations.

Kolmogorov-Smirnov test for normal distribution and heterogeneous dispersion test using Leven criteria will be also performed during every visit as additional assessments in FAS population for mean daily, mean daytime and mean nighttime number of urinations and urinary incontinence episodes at Weeks 2, 4, 8 and 12. In case when one of these tests is apparently statistically significant ($p < 0.05$), comparison between therapy groups will be performed using non-parametric Mann-Whitney criteria.

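### Change in OAB Awareness Tool and EQ-5D is tested without the Visit 2 score as covariate, which mis-corrects chance baseline imbalance and generally costs some precision

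*Combined protocol and SAP*

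**What the plan says.** Section 9.8 treats two families of efficacy endpoints differently.

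- **Diary counts** (urination and incontinence, including the primary variable) get ANCOVA with therapy group as factor. On the covariate: "Number of urinary incontinence episodes / urination at the Visit of start of therapy will be used as covariate".
- **Questionnaires** are taken separately: "Comparison of therapy groups on efficiency criteria: change in Overactive Bladder Awareness Tool Questionnaire (OAB Awareness Tool) and change in Quality of life" of life by EQ-5D "will be performed following data validation concerning their normality, distribution using Kolmogorov-Smirnov criteria". If the check is passed, Student's t-test is used; "otherwise non-parametric Mann-Whitney criteria will be used". No covariate is mentioned.

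The section also plans two-sided 95% confidence intervals for efficacy criteria other than the primary one, and analysis of the secondary criteria in both FAS and PP.

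The baseline scores exist. Section 4.5.3.2 lists both instruments among the Visit 2 procedures before randomisation: "Patient fills out OAB Awareness Tool Questionnaire and Quality of life Questionnaire EQ-5D". Section 4.5.5.6 confirms the schedule: "EQ-5D questionnaire is to be completed during randomization (Visit 2) and after the end of therapy" at Week 12, with the OAB Awareness Tool at screening and at Visits 2 to 6. Section 4.3.1 has no stratification beyond balance by centre, so the design does not balance these scores. No other section adds a baseline adjustment for the two questionnaires.

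**The concern.** The plan already holds the covariate and already uses the better method for the diary counts, yet gives no reason for leaving the questionnaires out. Three things follow.

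1. **Chance imbalance.** Taking change from Visit 2 imposes a baseline slope of 1. If the true slope is below 1, the group that happens to start worse appears to improve more. Inclusion criterion 5 requires a score of at least 8 at screening and at randomisation, so regression to the mean is to be expected for the OAB Awareness Tool.
2. **Precision.** Fixing the slope instead of estimating it generally widens the interval.
3. **A data-driven choice of test.** The OAB Awareness Tool is compared at four visits in two populations. The normality check could select a t-test in some of these and Mann-Whitney in others, so the reported quantity could change from one row of a table to the next. For the Mann-Whitney branch the plan names no effect measure or interval method.

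**Working it through.** **Reference sample size.** Section 9.2: 2 × 2.12² × (0.84 + 1.96)² / 0.8² = 2 × 4.4944 × 7.84 / 0.64 = 110.1, rounded up to 111 per group. The plan's figure is reproduced. It concerns the primary endpoint; the plan gives no calculation for the questionnaires. It serves below only as a reference size.

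**Variance formulas.** Let s0 and s1 be the baseline and follow-up SDs, k = s0/s1, and rho the baseline/follow-up correlation. Per patient, in units of s1² and ignoring the one degree of freedom spent on the covariate:

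- change score: k² + 1 − 2·rho·k
- ANCOVA: 1 − rho²
- difference: (k − rho)², which is never negative and is zero when k = rho.

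The slope that ANCOVA estimates is rho/k; the change score fixes it at 1. It over-corrects when rho < k and under-corrects when rho > k. With k = 1 the variance ratio ANCOVA/change is (1 + rho)/2.

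**Variance reduction from ANCOVA against the t-test on change** (rho and k are assumptions):

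| rho | k = 1 | k = 0.8 | k = 0.7 |
|---|---|---|---|
| 0.3 | 35% | 22% | 15% |
| 0.5 | 25% | 11% | 5% |
| 0.7 | 15% | 2% | 0% |

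Example, rho 0.5 and k 0.7: change 0.49 + 1 − 0.70 = 0.79; ANCOVA 0.75; 0.75/0.79 = 0.95.

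With k = 1, a change-score analysis would need 111 × 2/(1 + rho) = 171, 148 or 131 per group at rho 0.3, 0.5 or 0.7 to match ANCOVA with 111. Its interval is wider by a factor of 1.240, 1.155 or 1.085.

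**The only proxy for rho in the documents.** Section 2.2.6, Tables 2 to 4, gives SDs of urination frequency at baseline and of its 12-week change. With equal SDs, rho = 1 − SD(change)² / (2 × SD(baseline)²):

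- Table 2, imidafenacin: 1 − 1.70²/(2 × 2.28²) = 0.72
- Table 2, placebo: 1 − 1.62²/(2 × 2.50²) = 0.79
- Table 3: 1 − 2.12²/(2 × 2.81²) = 0.72
- Table 4: 1 − 1.70²/(2 × 2.44²) = 0.76

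The corresponding reduction, (1 − rho)/2, is about 10-14%. These are diary data, not questionnaire data.

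**Chance imbalance.** At 111 per group, a baseline difference of 1.96 standard errors is 1.96 × √(2/111) = 0.263 SD. With k = 1 the change-score comparison then carries a conditional bias of −(1 − rho) × 0.263 SD: −0.18, −0.13 and −0.08 SD at rho 0.3, 0.5 and 0.7. ANCOVA carries none under a linear model with a common slope.

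**Simulation of the planned two-stage procedure under no treatment difference** (normal data, 4,000 runs per setting, 111 per group):

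- Overall type I error: 0.052, 0.050 and 0.047 at rho 0.3, 0.5 and 0.7, so nominal.
- Among runs with baseline imbalance above 1.645 standard errors: 0.21, 0.14 and 0.10, against 0.05, 0.05 and 0.07 for ANCOVA. These runs are roughly a tenth of the total, about 400 per setting, so the Monte Carlo standard error near 0.05 is about 0.01.
- With a bounded 0-40 integer score floored at 8 at baseline (2,000 runs), overall error was 0.0445 to 0.053.
- The normality check sent fewer than 3% of null runs to Mann-Whitney in any setting, so these results describe essentially the t-test branch.

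**The case against.** The planned procedure is valid overall, the endpoints are secondary with no margin and no role in the sample size, and the gain may be small. All of that stands. Several stronger readings are tempting but not supported:

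- **A reader might infer that chance imbalance goes uncorrected.** It does not: the endpoint is change from Visit 2, so baseline is already subtracted. The defect is a fixed slope instead of an estimated one.
- **A reader might take 15-35% as the range of the gain.** It holds only for equal SDs and rho of 0.3 to 0.7. The entry threshold truncates the Visit 2 OAB Awareness Tool score and could make its SD smaller than at follow-up, which shrinks the gain; a ratio above 1 would raise it. The diary proxy also points to the low end. The formula does not apply to the Mann-Whitney branch at all.
- **A reader might infer inflated type I error.** The overall rate is nominal. It rises only conditionally on a marked imbalance.
- **A reader might infer that no interval can accompany Mann-Whitney.** The Hodges-Lehmann shift interval can; the plan simply does not name it.
- **A reader might infer that the diary counts are free of a normality switch.** The last paragraph of 9.8 puts them through Kolmogorov-Smirnov and Levene tests, with Mann-Whitney if either is significant, as additional assessments. The contrast drawn here is about the covariate in the main analysis.

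**Conclusion.** The point holds as a free improvement to two secondary endpoints. The plan omits a covariate that it collects before randomisation and uses the corresponding adjustment elsewhere. ANCOVA would remove the conditional bias from chance imbalance, given a linear relation with a common slope, and would never be materially less precise. The gain cannot be fixed from the documents because neither rho nor the SD ratio is given for either questionnaire: it could be anything from near zero to about a third of the variance over the values examined. Nothing here touches the primary non-inferiority conclusion, the 222/300 sample size or the overall validity of the planned tests.

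**What to change.** In section 9.8, for secondary criteria 7 and 8:

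- Analyse change in OAB Awareness Tool score (Weeks 2, 4, 8 and 12) and change in EQ-5D (Week 12) by ANCOVA, with treatment as factor and the Visit 2 value of the same measure as covariate.
- State that EQ-5D means the index and the VAS, each analysed with its own baseline. Section 2.4 describes both, but 9.8 does not say which is analysed.
- Report the adjusted difference with its two-sided 95% confidence interval in FAS and PP.
- Drop the Kolmogorov-Smirnov switch for these endpoints. Keep Mann-Whitney with a Hodges-Lehmann interval, or a bootstrap, as a sensitivity analysis only.

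The cost is a few lines of text. No data, visits or patients are added. Section 9.6 requires a protocol amendment for a change to the analysis plan; because the trial is open-label, it should be made before any comparison by group is run.

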	
Sample containing 222 patients (111 per study group) is considered to be sufficient for proof of alternative hypothesis (rejection of null-hypothesis) at the significance level 97.5% and study strength 80%. With due consideration of withdrawal during treatment total amount of patients to be randomized is about 300 (150 patients per study group).
 
For treatment efficiency assessment (primary endpoint) one-side 97.5% confidence interval for arithmetic mean values of primary endpoint will be calculated. In other cases of comparison two-sided 95% confidence intervals will be utilized.
 
Changes will be considered as significant at $p < 0.05$.
 
For comparison of AE appearance in the study groups χ^2 test of exact Fisher test is planned to be applied, for comparison of manifestation rate Mann-Whitney U test will be applied.
 
Laboratory parameters (total blood count and blood biochemistry, urinalysis), vital parameters will be assessed separately to each group with the following comparison using paired Student t-test for connected samples (for parameters with normal distribution) or using non-parametric Wilcoxon signed rank test for connected samples (for parameters with ordinary scale type or in case of significant distribution deviations from normal).

--	--

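### Section 9.8 does not say whether a test-triggered Mann-Whitney comparison replaces or supplements the ANCOVA bound that decides non-inferiority, and the level of that bound conflicts with sections 1.3, 9.2 and 9.3

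*Combined protocol and SAP*

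**What the plan says.** Section 9.8 assigns the diary endpoints, expressly including the primary one, to ANCOVA with the baseline count as covariate and treatment as factor. For the primary endpoint, "Primary efficiency analysis according to primary efficiency criteria will be performed in FAS and PP populations", and non-inferiority is judged by the "upper border of one-side 95% confidence interval for difference in evaluation of mean daily number of urinations". For the remaining endpoints, "During comparison of therapy groups according to other efficiency criteria two-sided 95% confidence intervals will be built".

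The last paragraph of 9.8 adds Kolmogorov-Smirnov and Levene tests, which "will be also performed during every visit as additional assessments in FAS population". They cover daily, daytime and night-time counts of urination and incontinence at Weeks 2, 4, 8 and 12. Should either test give a p-value below 0.05, the consequence is stated without qualification: "comparison between therapy groups will be performed using non-parametric Mann-Whitney criteria".

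The level of the deciding bound is stated differently elsewhere. The synopsis (section 1.3) says a "one-side 97.5% confidence interval for arithmetic mean values of primary endpoint will be calculated". Section 9.3 also gives one-sided 97.5%, and section 9.2 sizes the trial at a type I error of 0.025. The margin of 0.8 episodes per day is in the synopsis and section 9.2.

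**The concern.** Two analysts could follow this text in good faith and analyse the primary endpoint differently. One would report the ANCOVA bound and add a Mann-Whitney test beside it. The other would drop the ANCOVA bound once a pre-test is significant. Nothing says which result decides if they disagree, or how Mann-Whitney would use the 0.8 margin. The trial is open-label (section 4.3.2), so the reading could be settled with the results in view.

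Section 9.7 makes the FAS the lead efficacy set, with PP as confirmation, and the switch is written for the FAS. Under replacement, the lead analysis would ask whether the drugs differ at all, with no margin, no interval and no baseline adjustment. The PP method would also be open, because the switch names only the FAS while the general statement on normality in section 9.1.1 has no such limit.

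The two stated levels are a separate defect. They exist whatever the role of Mann-Whitney, but any sentence that fixes the deciding bound must also fix its level.

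**Working it through.** **1. The plan's own figure.** Inputs from section 9.2: margin 0.8, SD 2.12, one-sided alpha 0.025, power 80%, equal arms.

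n per arm = 2 × 2.12² × (0.84 + 1.96)² / 0.8² = 70.47 / 0.64 = 110.1, so 111 as stated. Power is 80.3% at 111 per arm and 90.5% at the 150 per arm randomised. The design therefore rests on a difference in means compared with 0.8.

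**2. What each procedure tests.** The null hypothesis in section 9.2 is that the difference is 0.8 or more; an upper bound below 0.8 rejects it. An ordinary Mann-Whitney tests no difference between distributions, and 0.8 does not enter. When the drugs are equal, a one-sided Mann-Whitney at 0.025 is significant in about 2-3% of trials, which is simply its alpha.

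**3. How often the switch would trigger.** For k independent tests at 0.05 on normal data with equal variances, the chance of at least one significant result is 1 − 0.95^k:
- k = 1 (Levene alone matters, if Kolmogorov-Smirnov is run without correction for estimated parameters and hardly ever rejects): 5.0%
- k = 2 (one pooled corrected Kolmogorov-Smirnov plus Levene): 9.75%
- k = 3 (corrected Kolmogorov-Smirnov in each arm plus Levene): 14.3%

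The plan does not say which version applies. Simulation over these versions gave 4.4-13.8% at 111 per arm for normal counts. For assumed gamma counts it gave 6.4-58.4% at 111 per arm and 7.9-71.9% at 150.

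**4. FAS success at true equality, under replacement only.** Assumptions:
- Week 12 count mean 11.56 − 1.65 = 9.91 (Table 3, section 2.2.6).
- SD 2.81, the Table 3 baseline value, taken as unchanged.
- Baseline correlation 1 − 2.12² / (2 × 2.81²) = 0.715, so that the change score has the plan's SD of 2.12.
- Success means the ANCOVA 97.5% bound is below 0.8 if not triggered, or a significant one-sided Mann-Whitney if triggered.

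With trigger rate t, success is approximately (1 − t) × ANCOVA power + t × 0.025. For normal counts with t = 0.138: 0.862 × 0.851 + 0.138 × 0.025 = 0.737. For gamma counts with t = 0.584: 0.416 × 0.847 + 0.584 × 0.025 = 0.367. Simulation (6,000 runs) agrees:

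| Counts | Per arm | ANCOVA alone | With replacement |
|---|---|---|---|
| Normal | 111 | 0.851 | 0.736-0.814 |
| Gamma | 111 | 0.847 | 0.370-0.800 |
| Normal | 150 | 0.940 | 0.814-0.899 |
| Gamma | 150 | 0.937 | 0.290-0.867 |

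ANCOVA alone exceeds 80.3% because it uses the baseline covariate.

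**5. Error control and level.** With a true deficit of exactly 0.8 and gamma counts (correlation parameter 0.5 or 0.7, 111 or 150 per arm, 10,000 runs), the ANCOVA 97.5% bound passes in 2.3-2.6% of trials and the 95% bound in 4.8-5.2%. A separate check with unequal SDs (3.5 and 2.3, equal arms) gave 2.4-2.6% at 97.5%. At one-sided 0.05 the formula would need 2 × 2.12² × (0.84 + 1.645)² / 0.64 = 86.7, so 87 per arm. The planned 111 matches the 97.5% level.

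**6. A rank analysis that does use the margin.** Mann-Whitney shifted by 0.8, on normal change scores with SD 2.12, has about 78% power at 111 per arm and 89% at 150, with error of 2.3-2.4%. On unadjusted counts with SD 2.8, power is only about 54% and 67%.

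**The case against.** The text favours a supplement. The ANCOVA sentence names the primary criterion; the last paragraph names neither that criterion nor non-inferiority nor the margin. It comes after the primary and secondary rules are complete, is introduced as also and additional, and is confined to the FAS, which would break the FAS-PP link of section 9.7 if it changed the method. Where section 9.8 clearly means substitution, for the questionnaires, it says so: "otherwise non-parametric Mann-Whitney criteria will be used". The Kolmogorov-Smirnov statement in section 9.1.1 that points towards replacement is generic and stands under data description. The English is also an awkward translation, so fine parsing carries limited weight. If Mann-Whitney only supplements, no harm follows.

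All of this stands as evidence of the likelier intent, but it does not settle the point. The word additional describes the two pre-tests, not the comparison that follows them. That comparison is stated as what will be performed, and the primary variable is not exempted. Sections 9 and 9.6 require deviations and plan changes to be reported or amended, but do not say which reading is the plan.

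It is also fair that the losses rest on several assumptions: the replacement reading, the gamma shape, an unchanged SD, the test version, and success defined as a one-sided superiority result, which the plan never states.

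Three stronger inferences are not supported:
- That the plan abandons the margin test for non-normal data. It nowhere says this.
- That a non-significant Mann-Whitney would be taken as non-inferiority. With a true deficit of 0.8 (normal data, SD 2.12, 111 per arm) about 22% of trials would be non-significant, but the plan states no such rule.
- That all incontinence intervals would be lost. Weekly incontinence at Week 12 is in the ANCOVA list but not in the pre-test list.

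**Conclusion.** The point holds as an unresolved ambiguity in the primary analysis, together with a plain contradiction over the level of the deciding bound. Both should be corrected before analysis.

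The ambiguity needs no distributional assumption: the trigger can fire on perfectly normal data, and the test it leads to cannot address 0.8. The size of the loss does rest on assumptions. The fall from about 85% to 74-81% or 37-80% at 111 per arm shows what replacement could cost; it is not a forecast for this trial. Under the supplement reading the loss is nil. In the cases checked, the switch is not needed to protect the error rate, since ANCOVA stayed near its nominal level under the assumed skew and under unequal variances.

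The level conflict stands independently: one-sided 95% would about double the false non-inferiority rate relative to the 0.025 used to size the trial.

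**What to change.** In section 9.8:
- State that the ANCOVA upper one-sided 97.5% bound, compared with 0.8, decides non-inferiority in both FAS and PP whatever the normality or variance tests show.
- Change the one-sided 95% level to 97.5%, in line with the synopsis and sections 9.2 and 9.3.
- Delete the test-triggered switch, or label Mann-Whitney as sensitivity only. If a rank analysis of the primary endpoint is kept, use a Hodges-Lehmann interval or a test shifted by 0.8, on change scores.
- Keep the two-sided 95% ANCOVA intervals for the other diary endpoints.

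The cost is wording, issued as the protocol amendment that section 9.6 requires for a change to the analysis plan. No new data, visits or patients are needed.
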